## 4. Objectives and Endpoints

**Table 4-1** **Objectives and Endpoints**

Objectives	Endpoints
Primary	
 
To compare the efficacy of AGN-242428 with placebo, administered orally once-daily for a period of 16 weeks, in participants with moderate to severe plaque psoriasis
 
The percentage of participants achieving a reduction (improvement) in Psoriasis Area and Severity Index (PASI) score of <math>\geq 75\%</math> from baseline to Week 16
 

Secondary	
 
To compare the efficacy of AGN-242428 with placebo, with respect to the Physician's Global Assessment (PGA) score
 
Percentage of participants achieving <math>\geq 2</math>-point improvement in PGA score at Week 16
 
To compare the efficacy of AGN-242428 with placebo, with respect to PASI score
 
Percentage of participants achieving a clear (0) or almost clear (1) score in PGA at Week 16
 
Percentages of participants achieving reductions of 50% and 90% from baseline in PASI at Week 16
 
To assess the safety and tolerability of AGN-242428 in participants with moderate to severe plaque psoriasis
 
Incidence of adverse events (AEs) including severity and causality of AEs, as well as AEs leading to discontinuation
 
Change from baseline in clinical laboratory tests, vital signs and electrocardiogram (ECG)
 
To characterize the pharmacokinetics of AGN-242428 in participants with moderate to severe plaque psoriasis
 
Plasma concentrations of AGN-242428 and pharmacokinetic parameters
 

AGN-242428

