**Clinical Hypotheses**

1. The percentage of participants achieving  $\geq 75\%$  reduction (improvement) in PASI score will be higher for AGN-242428-treated participants relative to placebo-treated participants.
2. AGN-242428 [REDACTED], [REDACTED] and [REDACTED] doses administered for 16 weeks will decrease clinical scores (eg, PASI, Physicians Global Assessment [PGA]) in participants with psoriasis to a greater extent than in participants receiving placebo.
3. AGN-242428 [REDACTED] dose administered for 16 weeks may decrease clinical scores in participants with psoriasis to a greater extent than treatment with [REDACTED] AGN-242428.
4. AGN-242428 at all 3 doses will be generally safe and well tolerated.

AGN-242428

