#### 5.5. Justification for Dose

The doses of AGN-242428 selected for this study are [REDACTED] once-daily for 16 weeks.

The [REDACTED] dose of AGN-242428 has been evaluated previously in healthy participants and patients for up to 28 days, and was shown to be generally safe and well tolerated. Administration for 28 days to patients with psoriasis resulted in an improvement in disease as measured by percent change from baseline in PASI scores. The [REDACTED] dose provided a plasma exposure that was  $\geq IC_{90}$  for inhibition of IL-17 secretion in an ex vivo whole blood assay of IL-17 secretion, and this inhibition was sustained over a full 24 hours duration with chronic dosing. Previous studies with multiple agents have demonstrated that it takes 12 to 16 weeks to see full efficacy for improvement in psoriasis. Thus, improvement from baseline in the PASI score at 28 days most likely does not represent the full potential for clinical efficacy. The current study (1957-201-001) extends the treatment duration to 16 weeks of once-daily dosing, providing the opportunity to more completely assess clinical efficacy at the 350 mg per day dose level.

The [REDACTED] and [REDACTED] doses of AGN-242428 allow for evaluation of a dose response. The [REDACTED] dose is expected to demonstrate improvement in disease as measured by change from baseline in the PASI score while maintaining a larger safety margin. The [REDACTED] dose is expected to demonstrate a greater improvement in disease than the lowest ([REDACTED] dose) as measured by change from baseline in the PASI score.

During the 4-week POC trial in participants with moderate to severe psoriasis (VTP-43742-002), elevations of ALT/AST were noted at a dose level of [REDACTED] but not at a dose level of [REDACTED]

AGN-242428

Selection of the [REDACTED] dose for evaluation in the current study thus provides a dose that has previously been demonstrated to be efficacious and to not have a liver function test (LFT) signal. Modeling of exposure and hepatic transaminase data from the VTP-43742-002 study suggest that a [REDACTED] dose is unlikely to result in elevations of hepatic transaminase levels greater than 3 x ULN for most participants. Given that the higher dose results in greater exposure, the [REDACTED] dose is expected to be more efficacious than the lower doses of [REDACTED] and [REDACTED].

AGN-242428

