### 10.3.2. Efficacy Analyses

#### 10.3.2.1. Primary and Secondary Endpoints

The following key primary and secondary efficacy endpoints will be analyzed for the mITT population. All other efficacy endpoints and analyses will be defined in the SAP.

The primary efficacy endpoint is the percentage of participants achieving a reduction (improvement) in PASI score of  $\geq 75\%$  from baseline to Week 16 (responder). The null hypothesis is that the population responder rates of the AGN-242428 and placebo groups are the same. The alternative hypothesis is that the rates differ:

- $H_0: r_v = r_p$
- $H_a: r_v \neq r_p$

where  $r_v$  and  $r_p$  are the population rates in the AGN-242428 and placebo groups, respectively.

The difference between each of the AGN-242428 groups and placebo in the proportion of participants with a reduction in PASI of  $\geq 75\%$  from baseline to Week 16 will be analyzed using a Chi-square test.

Frequency counts of participants achieving a 50%, 75%, and 90% reduction in PASI score relative to baseline will be tabulated by treatment at each postbaseline visit. Frequency counts of participants achieving  $\geq 2$ -point improvement in PGA score will be tabulated by treatment at each postbaseline visit. Frequency counts of participants who achieve a PGA score of clear or almost clear will be tabulated by treatment at each postbaseline visit.

Other efficacy measures will be summarized by visit and treatment.

AGN-242428

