10.1 PRIMARY EFFICACY PARAMETER

The primary efficacy endpoint will be percentage of participants achieving a reduction (improvement) in PASI score of $\geq 75\%$ from baseline to Week 16.

The null hypothesis is that the population responder rates of the AGN-242428 and placebo groups are the same. The alternative hypothesis is that the rates differ:

- $H_0: r_v = r_p$
- $H_a: r_v \neq r_p$

where r_v and r_p are the population rates in the AGN-242428 and placebo groups, respectively.

Frequency counts of participants achieving a $\geq 75\%$ reduction in PASI score relative to baseline will be tabulated by treatment at each postbaseline visit. The difference between each of the AGN-242428 groups and placebo in the proportion of participants with a reduction in PASI of $\geq 75\%$ from baseline, will be analyzed using a Chi-Square test.

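### Does the plan need a test that uses dose order because Protocol 5.5 speaks of evaluating a dose response?

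*SAP*

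**What the plan says.** Protocol 5.5 (Justification for Dose) says two of the doses "doses of AGN-242428 allow for evaluation of a dose response". It adds that one "dose is expected to demonstrate a greater improvement in disease than the lowest", and that another "dose is expected to be more efficacious than the lower doses of" the remaining two. The Clinical Hypotheses in Protocol 4 say the three "doses administered for 16 weeks will decrease clinical scores" more than placebo, and that one dose "may decrease clinical scores in participants with psoriasis to a greater extent than treatment with" another active dose.

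The primary objective in Protocol Table 4-1 is a comparison with placebo: "To compare the efficacy of AGN-242428 with placebo, administered orally once-daily for a period of 16 weeks". SAP 5.0 likewise lists efficacy against placebo, safety and pharmacokinetics. The two main questions in Protocol 5.4 are efficacy relative to placebo and safety. None of these lists names dose response.

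On analysis, Protocol 10.3.2.1 specifies the primary test and says "All other efficacy endpoints and analyses will be defined in the SAP". SAP 10.1 and 10.2 tabulate responders by treatment at each postbaseline visit. For PASI-75, "The difference between each of the AGN-242428 groups and placebo in the proportion of participants" who respond is then tested by chi-square, and the four secondary endpoints are tested in the same way. Protocol 10.3.5 adds graphs of efficacy against AUC and Cmin, followed by nonlinear mixed effects modelling if a trend is seen, all to be prespecified in a pharmacometrics analysis plan.

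**The concern.** A Phase 2b trial with three active doses is normally read for its dose response, and Protocol 5.5 and the third hypothesis both speak of one dose doing better than another. Protocol 10.3.2.1 defers further efficacy analyses to the SAP, and the readable SAP has no trend test, ordered contrast, dose-response model or comparison between active doses.

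Two things would be at stake. First, if the method for judging dose response were chosen after unblinding, a favourable one could be picked. Second, separate tests can give a mixed result (one or two of three doses significant), and the plan gives no rule for reading it.

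**Working it through.** **Inputs.** Placebo response 6%, difference 27 points (so 33% on active), two-sided 5%, 50 per arm and 20% dropout come from Protocol 10.1 and SAP 14.0; 50 × 0.8 = 40 per arm. Doses 225, 350 and 450 mg come from SAP 4.0. The documents give no response rate by dose, so every pattern below other than 33% against 6% is an assumption. Tests are uncorrected Pearson chi-square.

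**1. The plan's own figure.** Unpooled standard error = √(0.06×0.94/40 + 0.33×0.67/40) = 0.0833. Then 0.27/0.0833 = 3.24, and power = Φ(3.24 − 1.96) = 90.0%. Exact binomial power of the chi-square test is 90.4%. The pooled formula gives 87.6%. The stated 90% is reproduced, and it belongs to the tests that SAP 10.1 names.

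**2. Would a trend test across all four arms show dose order?** The Cochran-Armitage numerator is proportional to Σ pᵢ(dᵢ − d̄). Scores 0/225/350/450 have mean 256.25, so the weights are −256.25, −31.25, 93.75 and 193.75.

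- Rising pattern 6/15/24/33%: −15.375 − 4.6875 + 22.5 + 63.9375 = 66.375.
- Flat active doses 6/33/33/33%: 256.25 × (0.33 − 0.06) = 69.1875.

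The contrast is slightly larger when the active doses are identical. It is driven by placebo against the rest. Power is 92.5% in the rising pattern and 90.2% in the flat one, so rejection does not separate the two.

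The result also depends on the scores. With equal spacing, power falls from 90% to 78% in the flat case and from 51% to 25% at 33/33/20%.

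**3. Would a test on active doses only do it?** Mean score 341.67; weights −116.67, 8.33 and 108.33.

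- Flat 33%: the contrast is 0, and the test rejects 5.0% of the time.
- 15/24/33%: −17.5 + 2.0 + 35.75 = 20.25. The expected statistic is 40×20.25/√(0.24×0.76×40×25416.7) = 1.88, so power = Φ(1.88 − 1.96), about 47%.

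Across the four rising patterns examined (15/24/33, 20/27/33, 27/33/40 and 33/40/45%) power is about 20-47%. This is the test that addresses order among doses, and the trial is not sized for it.

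**4. How large is the risk from choosing a method afterwards?** With no drug effect and a 6% rate, one named trend test rejects 4.9% of the time. The chance that at least one of several tests rejects depends on which are assumed to be on offer:

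| Tests assumed available | Any rejects |
|---|---|
| Trend with dose scores, trend with equal scores | 5.6% |
| As above plus active-only trend | 9.2% |
| As above plus pooled active against placebo | 11.0% |

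None of these tests is in the documents, and the pooled comparison does not use dose order. In every case the primary tests are already fixed.

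**5. Mixed results.** One or two of three doses are significant in 69%, 52%, 28% and 11% of trials in the four rising patterns, and in 20% if all are 33%. The chance that any dose is significant with no effect is 12.9%. A supportive trend test alters neither set of figures, because the three dose tests would stay as they are.

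**The case for a change.** The strongest case for the concern is that Protocol 5.5 gives dose response as a reason for choosing the doses, a numbered hypothesis compares active doses, and the exposure-response work does not fill the gap exactly. It uses AUC and Cmin rather than randomized dose, its modelling depends on a trend first being seen in graphs, and SAP 4.0 places it in a separate document. One supportive test, fixed before unblinding, would cost a paragraph.

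Those facts are correct, and no readable efficacy analysis uses dose order. What does not follow is that the plan is deficient. Saying that doses permit an evaluation is not a commitment to an ordered test, and the third hypothesis is worded as a possibility. The between-dose expectations in Protocol 5.5 concern change in PASI score and the third hypothesis concerns clinical scores, so a trend test on PASI-75 response across placebo and the doses would answer neither.

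Two smaller remarks stand without changing the conclusion. The null in SAP 10.1 carries no dose subscript, but the sample-size statement and the test description show that it applies to each dose, so this is editorial. SAP text after 11.4 is blacked out and table specifications are a separate document, so absence can be claimed only for the readable text.

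**Conclusion.** The concern does not hold. The tests in SAP 10.1 match the primary objective and the sample size, and they stay sound if the plan is followed as written. Dose response is design rationale here; by-dose tables and the separately prespecified exposure-response analysis serve it.

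A trend test that includes placebo would reject about 90% of the time with identical active doses. An active-only test would have about 20-47% power in the rising patterns assumed. Neither would change a primary conclusion. The added error from choosing a method afterwards runs from 5.6% to 11.0%, depending on a list of tests that the plan does not contain.

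These figures assume 40 per arm, 6% placebo response, uncorrected chi-square and illustrative rates by dose. The reading of the documents does not depend on them.

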10.2 SECONDARY EFFICACY PARAMETERS

The following are considered secondary endpoints of the study:

- Percentage of participants achieving ≥ 2 -point improvement in PGA score at Week 16
- Percentage of participants achieving a clear (0) or almost clear (1) score in PGA at Week 16

- Percentages of participants achieving reductions of 50% from baseline in PASI score at Week 16
- Percentages of participants achieving reductions of 90% from baseline in PASI score at Week 16

Frequency counts of participants achieving \geq 2-point improvement in PGA score will be tabulated by treatment at each postbaseline visit. Frequency counts of participants who achieve a PGA score of clear or almost clear will be tabulated by treatment at each postbaseline visit. Frequency counts of participants achieving a 50% and 90% reduction in PASI score relative to baseline will be tabulated by treatment at each postbaseline visit.

The difference between each of the AGN-242428 groups and placebo in the proportion of participants achieving each of the secondary endpoints above will be analyzed using a Chi-Square test.

11.0 SAFETY ANALYSES

The safety analysis will be performed using the Safety Population. The safety parameters will include adverse events (AEs) and clinical laboratory, vital sign, and electrocardiographic (ECG) parameters. For each safety parameter of the clinical laboratory, vital sign, and ECG parameters, the last nonmissing safety assessment before the first dose of study treatment will be used as the baseline for all analyses of that safety parameter. Continuous variables will be summarized by number of participants and mean, SD, median, minimum, and maximum values. Categorical variables will be summarized by number and percentage of participants.

11.1 ADVERSE EVENTS

Adverse events will be coded by SOC and PT using the MedDRA, version 20.1 or newer.

An AE will be considered a treatment-emergent adverse event (TEAE) if the AE began or worsened (increased in severity or became serious) on or after the date of the first dose of study intervention. Per case report form instructions, a new AE record will be created for any AE that worsens; therefore, TEAEs can be identified as those AEs with recorded onset date on or after the date of the first dose of study intervention

The number and percentage of participants reporting TEAEs will be summarized by treatment group using MedDRA PT nested within SOC. Events will be in alphabetic order of SOC and by descending frequency of PTs within each SOC. Treatment-related TEAEs will be tabulated by descending frequency of PTs within the SOC. If more than 1 AE is coded to the same PT for the same patient, the patient will be counted only once for that PT using the greatest severity and strictest causality for the summarization by severity and causal relationship.

The number and percentage of participants who have treatment emergent serious adverse events (TESAEs) will be summarized by PT and treatment group.

The number and percentage of participants in the Safety Population who have TEAEs leading to premature discontinuation of the study treatment will be summarized by PT and treatment.

11.1.1 Adverse Events of Special Interest

The following adverse events of special interest (AESI) will be summarized by treatment group:

- aspartate aminotransferase (AST) and/or alanine aminotransferase (ALT) $\geq 5 \times$ upper limit of normal (ULN)
- AST and/or ALT $\geq 3 \times$ ULN AND total bilirubin (TBL) $\geq 2 \times$ ULN or international normalized ratio (INR) > 1.5
- AST and/or ALT $\geq 3 \times$ ULN with symptoms believed to be related to liver injury (eg, fatigue, nausea, vomiting, right upper quadrant pain or tenderness or jaundice) or hypersensitivity (such as fever, rash, or eosinophilia $> 5\%$)
- Changes in hepatic laboratory test results that meet potential Hy's Law
 - ALT and/or AST $\geq 3 \times$ ULN AND
 - TBL $\geq 2 \times$ ULN AND
 - Alkaline phosphatase $< 2 \times$ ULN

Potential Hy's Law criteria within a 24-hour window is defined by a postbaseline elevation of ALT and/or AST $\geq 3 \times$ ULN, along with TBL $\geq 2 \times$ ULN and a non-elevated alkaline phosphatase (ALP) $< 2 \times$ ULN, all based on blood draws collected within a 24-hour period.

A graphical representation of liver function, known as eDISH, will be generated by plotting the maximum postbaseline TBL elevation at any timepoint during the study vs maximum postbaseline ALT elevation at any timepoint. Note that the maximum ALT may be from a different visit than when the maximum TBL was observed. A plot of maximum TBL vs maximum AST will be generated separately.

11.2 CLINICAL LABORATORY PARAMETERS

Descriptive statistics (mean, SD, median, Q1, Q3, minimum, and maximum) for clinical laboratory values (in SI units) and changes from the baseline values at each assessment timepoint will be presented by treatment group for the following laboratory parameters:

Table 11.2-1 Clinical Laboratory Tests

Category ^a	Parameters
Hematology and Coagulation^a	Hematocrit (HCT), hemoglobin (HGB), red blood cell (RBC) count, RBC indices, total leukocyte (or white blood cell [WBC]) count including differential, and platelet count with mean platelet volume, activated partial thromboplastin time (aPTT), prothrombin time (PT), international normalized ratio (INR)
Serum Chemistry	
Electrolytes	Sodium (Na), potassium (K), chloride, bicarbonate
Renal function	Blood urea nitrogen (BUN), creatinine (Cr)
Liver function ^a	ALT, AST, ALP, total, direct, and indirect bilirubin (TBL, DBL, IBL), gamma-glutamyl transferase (GGT), lactate dehydrogenase (LDH)
Pancreatic function	Lipase and amylase
Other ^a (selected tests at Week 6 and Week 10)	Calcium (Ca), magnesium (Mg), phosphorus (P), total protein ^a , albumin ^a , globulins, glucose, uric acid, creatine phosphokinase (CK) ^a , cholesterol (total and fractionated) and triglycerides
Urinalysis	Appearance, bilirubin, color, ketones, glucose, leukocyte esterase, nitrites, pH, blood, protein

^a Visits on Week 6 and Week 10 need random blood draws. Participants can be fasting or non-fasting and only the following laboratory tests will be performed at those visits: Hematology and Coagulation, Liver function, and Other (Total protein, albumin, and CK)

Clinical laboratory test values will be considered potentially clinically significant (PCS) if they meet either the lower-limit or higher-limit PCS criteria listed in [Table 11.2-2](#). A listing of patients with PCS postbaseline values will be provided, including the participant identification (PID) number, baseline, and all postbaseline (including non-PCS) values.

Table 11.2-2 Criteria for Potentially Clinically Significant Laboratory Results

Parameter	Unit	Lower Limit	Higher Limit
CHEMISTRY			
Albumin	g/dL	≤ 2.0	≥ 7.1
Alanine aminotransferase	U/L	—	≥ 3 x ULN
Alkaline phosphatase	U/L	—	> 2 x ULN

Table 11.2-2 Criteria for Potentially Clinically Significant Laboratory Results

Parameter	Unit	Lower Limit	Higher Limit
Amylase	U/L	—	> 1.5 x ULN
Aspartate aminotransferase	U/L	—	≥ 3 x ULN
Bicarbonate	mEq/L	≤ 15	≥ 40
Bilirubin, total	mg/dL	—	≥ 2.75 x ULN
Calcium	mg/dL	< 7.0	> 12.5
Chloride	mEq/L	≤ 74	≥ 131
Cholesterol	mg/dL	—	> 400
CPK	U/L	—	> 2.5 x ULN
Creatinine	mg/dL	—	≥ 2 x ULN
GGT	U/L	—	≥ 2.5xULN
Glucose	mg/dL	< 55	> 250
LDH	U/L	—	≥ 2 x ULN
Lipase	U/L	—	> 2 x ULN
Magnesium	mEq/L	< 1.0	> 2.5
Potassium	mEq/L	< 3.0	> 6.0
Phosphorus	mg/dL	< 2.0	≥ 9.4
Protein, total	g/dL	≤ 3.9	≥ 10.1
Sodium	mEq/L	< 130	> 155
Triglycerides	mg/dL	—	> 300
BUN	mg/dL	—	> 31
Uric acid	mg/dL	—	> ULN
HEMATOLOGY			
Eosinophils, absolute cell count	x10E3/uL	—	> ULN
Eosinophils	%	—	> ULN
Neutrophils, absolute cell count	x10E3/uL	< 1.5	≥ 2 x ULN
Neutrophils	%	< LLN	> ULN

Table 11.2-2 Criteria for Potentially Clinically Significant Laboratory Results

Parameter	Unit	Lower Limit	Higher Limit
Lymphocytes, absolute count	$\times 10^3/\mu\text{L}$	< 0.8	> 4
Lymphocytes	%	< LLN	> ULN
Haematocrit	%	< 20	> 60
Haemoglobin	g/dL	< 8.0	≥ 19
INR	—	—	> 1.5
Platelet count	$\times 10^3/\mu\text{L}$	< 100	> 999
White blood cell count	$\times 10^3/\mu\text{L}$	< 3.0	≥ 22
URINALYSIS			
pH	—	< LLN	> ULN
Specific gravity	—	< LLN	> ULN
Blood	—	—	$\geq 2+$
Protein	—	—	$\geq 2+$
Glucose	—	—	$\geq 2+$

LLN = lower limit of normal value provided by the laboratory; ULN = upper limit of normal value provided by the laboratory.

11.3 VITAL SIGNS

Descriptive statistics (mean, SD, median, Q1, Q3, minimum, and maximum) for vital signs (systolic and diastolic blood pressures, pulse rate, and weight) and changes from baseline values at each visit and at the end of study will be presented by treatment group.

Vital sign values will be considered PCS if they meet both the observed-value criteria and the change-from-baseline criteria listed in Table 11.3-1. A listing of patients with PCS postbaseline values will be provided, including the PID number, baseline and all postbaseline (including non-PCS) values.

Table 11.3–1 Criteria for Potentially Clinically Significant Vital Signs

Parameter	Flag	Criteria^a	
		Observed Value	Change From Baseline
Sitting systolic blood pressure, mm Hg	High	≥ 180	Increase of ≥ 20
	Low	≤ 90	Decrease of ≥ 20
Sitting diastolic blood pressure, mm Hg	High	≥ 105	Increase of ≥ 15
	Low	≤ 50	Decrease of ≥ 15
Sitting pulse rate, bpm	High	≥ 120	Increase of ≥ 15
	Low	≤ 50	Decrease of ≥ 15
Weight, kg	High	—	Increase of ≥ 7%
	Low	—	Decrease of ≥ 7%

a A postbaseline value is considered potentially clinically significant if it meets both the observed-value and the change-from-baseline criteria.

bpm = beats per minute.

